#### 4.3.1 Bleeding

Aggrenox has a small dose of aspirin that will increase the risk of bleeding. Bleeding will be classified as either minor, intermediate, major, life-threatening or fatal. Minor bleeding events are episodes of bleeding that did not require an event-related visit or follow-up or discontinuation of the study drug. Intermediate bleeding is a bleeding event that does not meet criteria for a major bleed but required an event-related visit with a health care provider or temporary discontinuation of study medication. Examples of minor or intermediate bleeds might include superficial cuts, abrasions, bruises, nose bleeds, or vaginal bleeding events. The presence of a hemoccult positive stool alone that leads to non-emergent evaluation such as a colonoscopy and is not associated with a 2 g/dl drop in hemoglobin or the need for a transfusion will be considered an intermediate bleeding event. Major bleeding is defined as a confirmed retroperitoneal, intra-articular, intraocular, or intracranial bleed or any bleed that leads to a drop in hemoglobin by 2 g/dl and requires hospitalization or the need for a transfusion, causes a symptomatic intracranial hemorrhage, or requires a transfusion of more than 4 units of packed RBCs or whole blood. Fatal bleeding is any bleed that causes or precipitates death.

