# 6.2.2 All Monthly Visits

- 1. Access recirculation and access blood flow within first 2 hours of dialysis (see Manual of Operations)
- 2. Blood pressure (sitting) predialysis (from chart) and at time of access blood flow
- 3. Person doing needle insertion (patient or nurse).
- 4. Problems with needle insertion in the last month (hematomas, multiple needle sticks, failed insertions)
- 5. Access related events (see list in Section 12.1)
- 6. Access related procedures (see list in Section 12.2) indication, date of procedure, outcome
- 7. Hospitalizations primary and secondary diagnosis, dates of admission and discharge
- 8. Compliance with study medications as assessed by patient interview and monthly pill count. Subjects will be asked to return pill bottles of study medication each month.
- 9. Current medications.
- 10. Monthly dialysis lab tests serum albumin, hemoglobin, hematocrit, pre and post BUN, calcium, phosphorus. PTH when available every third month.
- 11. For incident patients not yet on dialysis the patency of the access will be determined by the presence of an audible bruit or a palpable thrill in the graft.
- 12. Adverse event monitoring (see Section 6.2.3 below)

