# 6.2.3 Monthly Adverse Event Monitoring

Adverse events will be recorded at the monthly visits. Subjects will be asked the following questions:

- 1. Have you had any problems with your study medication? Describe them.
- 2. Have you had any hospitalizations? When and what was the reason?
- 3. Have you had any other new significant health problems? Describe them.
- 4. Have you had any episodes of significant bleeding?
- 5. Are you having any gastrointestinal symptoms such as heartburn or abdominal pain?

The responses to all these questions will be recorded and an assessment will be made as to whether the event is related to the study medication. For any hospitalizations or emergency room visits the medical record will be reviewed to determine the cause of the visit and whether it was likely related to the study medication. Particular attention will be given to whether a bleeding event precipitated the visit or hospitalization. For patients that might be questionable historians, the dialysis nurse caring for the patient will be asked whether they are aware of any adverse events, hospitalizations, or transfusions that have occurred in the preceding month. In addition, the patient dialysis logs will be examined to determine if the patient missed any sessions and the patient will be asked the reason for the absence. Serious adverse events are those that result in any of the following outcomes: death, a life-threatening adverse experience, inpatient hospitalization or prolongation of existing hospitalization, a persistent or significant disability/incapacity, or a congenital anomaly or birth defect. All serious adverse events will be reported to the DCC within 24 hours of study personnel learning of the event.

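### A bleed the patient does not notice, transfused outside hospital or emergency room, has no stated route of detection: transfusions are asked about only for some patients, and a hemoglobin fall prompts no query

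*Protocol*

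**What the plan says.** **Definition (Protocol 4.3.1).** A major bleed includes "any bleed that leads to a drop in hemoglobin by 2 g/dl and requires hospitalization or the need for a transfusion". The other routes to the major class are a named site, symptomatic intracranial hemorrhage, or transfusion of more than 4 units. The same two markers serve again lower down: a hemoccult-positive stool that "is not associated with a 2 g/dl drop in hemoglobin or the need for a transfusion will be considered an intermediate bleeding event".

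**What every patient is asked (Protocol 6.2.3).** There are five monthly questions. They include "Have you had any episodes of significant bleeding" and "Have you had any hospitalizations? When and what was the reason", and also cover gastrointestinal symptoms, problems with the study medication and other new health problems. None mentions transfusion.

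**Record review (Protocol 6.2.3).** "For any hospitalizations or emergency room visits the medical record will be reviewed to determine the cause of the visit", with particular attention to bleeding.

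**The query that names transfusions (Protocol 6.2.3).** It opens "For patients that might be questionable historians" and continues that "the dialysis nurse caring for the patient will be asked whether they are aware of any adverse events, hospitalizations, or transfusions".

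**Laboratory data (Protocol 6.2.2).** The list for all monthly visits includes "Monthly dialysis lab tests serum albumin, hemoglobin, hematocrit". No section makes a fall in hemoglobin the occasion for a bleeding query.

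**The concern.** Transfusion and a 2 g/dl hemoglobin drop are what make a bleed major when it has no special site and no hospital stay. Transfusion is sought only in patients whom site staff judge to be doubtful reporters, and that judgement can differ between centers. Hemoglobin is in the database but is not used to look for bleeds.

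Bleeding is the main expected risk of the drug (section 6.2.6). In the hypertension trial cited in section 1.5, gastrointestinal bleeds were 72 of 129 non-fatal major bleeds on aspirin and 34 of 70 on placebo, and such a bleed can be slow and unnoticed. If one is missed, the adverse-event comparison that goes to the External Advisory Committee (section 10) is incomplete. The protocol's own provisions for study drug after a major bleed (sections 4.3.1 and 4.3.6) are then not considered for that patient.

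**Working it through.** The protocol states no figure on this point, so the check compares the major-bleed criteria with each route by which a bleed could be found.

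1. **Major bleed with a hospital stay or emergency visit.** Covered in all patients by record review, once the visit is known. A transfusion given there is covered too.
2. **Bleed the patient notices.** Covered by the bleeding question, and partly by the question on gastrointestinal symptoms.
3. **Unnoticed bleed, 2 g/dl drop, transfused outside hospital and emergency room, patient regarded as a doubtful historian.** Covered by the nurse query.
4. **The same bleed in any other patient.** No question names the transfusion, no visit opens a record review, and the recorded hemoglobin prompts nothing.

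Other safeguards do not clearly reach route 4:

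- The dialysis logs are examined for missed sessions (6.2.3).
- The definition of a serious adverse event (6.2.3 and 10) does not list transfusion, so such a bleed need not be an expedited report unless it is life-threatening.
- The expert panel (4.3.1) and the review of deaths within 30 days of a bleed (6.2.6) act on bleeds already recorded.
- Section 4.3.1 says bleeding will be actively monitored but gives no method.

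Route 4 may be wider for patients not yet on dialysis, who may have neither a dialysis nurse nor monthly dialysis laboratory tests. That is an inference.

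**How many major bleeds are at issue in all.** This gives scale only. Inputs from section 9.1: 1056 subjects (528 per arm), one-year failure 0.54, a 25% reduction, 22% annual loss, 3 years of accrual and 4 years in total. Assumptions: uniform accrual, constant hazards, and bleeding follow-up counted to the first access event.

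- Hazards per year: failure on placebo −ln(0.46) = 0.777; on drug 0.75 × 0.777 = 0.582; loss −ln(0.78) = 0.248.
- Mean follow-up with total hazard h: (1/h) × [1 − (e^(−h) − e^(−4h))/(3h)].
- Placebo, h = 1.025: 0.867 years × 528 = 458 patient-years.
- Drug, h = 0.831: 1.011 years × 528 = 534 patient-years.
- Section 1.5 gives 1–1.5% serious hemorrhage per year on placebo in hemodialysis patients: 458 × 0.010 to 0.015 = 4.6 to 6.9 events.
- A 2-fold rise on drug gives 534 × 0.020 to 0.030 = 10.7 to 16.0 events. A 4-fold rise, the top of the range in section 1.5, gives 534 × 0.040 to 0.060 = 21.4 to 32.0.

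With the extension in the section 9.1 addendum (48 months of recruitment plus 6 months), the patient-years become about 441 and 514, which changes these counts little.

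**Effect of missing some.** If a share f of major bleeds is missed in both arms, the observed difference is (1 − f) times the true difference and the ratio is unchanged. The protocol gives no value for f.

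**The case against.** The strongest reply is that the gap is narrow. To escape, a bleed must be unnoticed, drop hemoglobin by 2 g/dl, be transfused outside hospital and emergency room, not surface under the question on new health problems, and occur in a patient not regarded as a poor historian. The coordinator also has a general duty to monitor bleeding. The data forms and the Manual of Operations are not shown and might contain a transfusion item. The narrowness stands, and it fixes the scope of this point. The unseen documents do not remove it: section 6.2.3 does not defer to the manual, and it states a restriction rather than staying silent.

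A reader might infer more than the text supports:

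- *That occult major bleeds in general go unrecorded.* They do not: record review covers hospital and emergency care.
- *That a 2 g/dl fall or a transfusion is enough for a major bleed.* Section 4.3.1 requires the fall together with hospitalization or need for transfusion, unless another criterion is met.
- *That hemoglobin is unconnected to bleeding.* Section 4.3.1 uses it twice and section 6.2.2 collects it. Only a trigger is missing.
- *That the treatment comparison is biased.* Patients and staff are masked (3.4) and randomization is stratified by center (3.3), so uneven use of the nurse query should fall on both arms alike.
- *That a percentage missed can be stated.* The documents contain none. Even the 4-fold count above is doubtful: that range comes from a stroke trial, while section 1.5 reports about 2-fold in the graft study, and says that about 30% of surveyed hemodialysis patients already take aspirin and are not expected to bleed more.

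**Conclusion.** The point holds in a limited form. One kind of major bleed has no stated route of detection: unnoticed by the patient, transfused outside hospital and emergency room, in someone not regarded as a doubtful historian. Major bleeds may therefore be under-counted, probably to a similar degree in both arms. That would shrink the absolute excess on drug while leaving the ratio about the same.

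The amount cannot be computed from the protocol. With only about 5 to 7 serious bleeds expected on placebo under the planning figures, a few missed events would still matter to the safety record. The conclusion assumes that the protocol text is what sites follow, and that no unseen form already asks every patient about transfusion. The primary efficacy analysis is not affected.

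**What to change.** In section 6.2.3, remove the restriction on the transfusion query. Record transfusions in the preceding month for every patient at every monthly visit, from the patient and from the dialysis nurse or dialysis record.

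Have the DCC issue a query for possible bleeding when consecutive monthly hemoglobin values fall by 2 g/dl or more. State that this prompts review and does not classify a major bleed; the criteria in section 4.3.1 still decide that.

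The cost is one form item, one automated check on data already collected, and additional queries, some of which will turn out to be anemia without bleeding. The protocol gives no basis for estimating their number. No dose, stopping rule, sample size or alpha changes.

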#### 6.2.4 Every Third Month

Response to quality of life questions will be obtained (71, 72).

#### 6.2.5 Blood and DNA Collection

Blood and DNA samples will be collected for use in future research studies to assess risk factors for access failure and response to therapy. A sample will be collected once for each patient, preferably at the baseline visit. For those patients where this is not possible, collect the blood at the next possible visit.

#### 6.2.6 Quality Control of Clinical Center Data

Each clinical study site will be visited once during year one and every other year for the remainder of the study. The site visit will consider recruitment, retention, patient compliance, adverse event monitoring and clinical center adherence to study procedures. During the data audit portion of the site visit, site visitors will examine a random subset of site clinical data for which source documentation would normally be available, such as date of birth and local laboratory data. Data on source documents at the clinical center will be compared with data in the DAC Study Database.

Bleeding is the major expected risk of therapy with Aggrenox. For purposes of safety and adverse event analyses, categorization of bleeding events will be made based on information transmitted from the clinical centers on the data forms with additional information obtained from source documents as needed. To assure that bleeding events that result in death are properly documented there will be central review of data on any subject who has had a bleeding event recorded in the study database within 30 days prior to death. The study's Data Coordinating Center will notify investigators about any subject who meets these criteria. The center will then send primary data including any emergency room or hospital discharge summaries relevant to the bleed as well as documentation relating to the subsequent death. This information will be reviewed by two independent physician study investigators to determine whether the cause of death was related to the prior bleed.

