Management of bleeding should be handled as for a patient on aspirin. For minor episodes of bleeding (e.g., superficial abrasion or nose bleed) conservative measures to control the bleeding should suffice without the requirement for discontinuing study medication. Short-term discontinuation of study medication during an intermediate bleeding episode with re-institution when stable is allowed. If the patient has a major or life-threatening bleed the study medication will be discontinued and not restarted. In the event of a cerebrovascular accident occurring during active treatment, computed tomography or magnetic resonance imaging should be performed to exclude intracerebral hemorrhage. For intermediate bleeds the decision to stop study drug will be made by the physician(s) caring for the patient. If the patient has a major or life-threatening bleed the study medication will be discontinued and not restarted unless the bleed is caused by either a surgical procedure or trauma and it is established 1) that the cause of bleeding has been eradicated, and 2) that the bleeding event does not reflect an underlying bleeding tendency or predispose to recurrent bleeding. Study drug resumption in this situation must be approved by the physician(s) caring for the patient. Bleeding events will be actively monitored and recorded by the study coordinator throughout the patient's participation on the study. An expert panel will review all major and life-threatening bleeds as well as a randomly selected subset of other bleeding events.

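### The central review of bleeding-related death covers only deaths with a bleed recorded in the prior 30 days, which is narrower than the protocol's own definition of a fatal bleed

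*Protocol*

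**What the plan says.** Protocol section 4.3.1 grades bleeds and defines the top grade causally: "Fatal bleeding is any bleed that causes or precipitates death". It sets no interval between bleed and death and requires no prior database entry.

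Section 6.2.6 takes the grade of a bleed from what the center sends: "categorization of bleeding events will be made based on information transmitted from the clinical centers on the data forms", supplemented by source documents where needed. It then adds a central check on deaths. The purpose is stated as "To assure that bleeding events that result in death are properly documented", and the check applies to "any subject who has had a bleeding event recorded in the study database within 30 days prior to death". For those subjects the center sends its records, and the task is fixed as follows: "This information will be reviewed by two independent physician study investigators to determine whether the cause of death was related to the prior bleed".

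Three other provisions bear on the point:

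- Section 4.3.1 has a second central review: "An expert panel will review all major and life-threatening bleeds as well as a randomly selected subset of other bleeding events".
- Section 6.2.3 says how events are collected: "Adverse events will be recorded at the monthly visits. Subjects will be asked the following questions". It also requires the medical record to be read for each hospitalization or emergency visit: "Particular attention will be given to whether a bleeding event precipitated the visit or hospitalization".
- Sections 6.2.3 and 10 make death a serious adverse event, to be reported to the data coordinating center within 24 hours of study personnel learning of it.

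**The concern.** The aim of the section 6.2.6 review is to get deaths from bleeding properly documented, yet its entry condition depends on a bleed record from the preceding month. Two kinds of death can meet the section 4.3.1 definition without meeting that condition. One is a death that follows a recorded serious bleed by more than 30 days. The other is a death attributed to hemorrhage, stroke, or sudden or unknown cause for which no bleeding event was separately recorded.

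Bleeding is named in section 6.2.6 as the main expected risk of the active drug, and section 8.2 predicts no increase in serious or fatal bleeds. The fatal-bleed count is the direct test of that prediction. It will be small, so whether one or two deaths are correctly attributed matters to how the safety result reads.

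**Working it through.** No sample-size or power figure in the protocol depends on this point, so the main check is to set the definition and the trigger side by side. The arithmetic below gives only the scale.

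**1. Coverage of the trigger**

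| Death | Can meet the 4.3.1 definition? | Sent for cause-of-death review under 6.2.6? | Other central look? |
|---|---|---|---|
| Any recorded bleed, 30 days or less before death | Yes | Yes | Panel, if major or life-threatening |
| Recorded major bleed, death on day 35 | Yes | No | Panel reviews the bleed; not asked about the death |
| Reported as hemorrhage or stroke, no separate bleed record | Yes | No | None stated |
| Sudden or unknown cause, no bleed record | Yes | No | None stated |

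The trigger also takes no account of severity. A nosebleed 20 days before death brings the case in, while an intracranial bleed 35 days before death does not. The protocol gives no reason for the 30-day limit.

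**2. Which date counts**

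The trigger wording does not say whether the 30 days apply to the date of the bleed or to the date it was entered. If the bleed date counts, a terminal bleed learned of through the death report and entered afterwards would qualify. If the entry date counts, it would not.

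**3. Scale of the fatal-bleed count**

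Inputs: 1056 subjects allocated 1:1 (section 2.2), so 1056 / 2 = 528 per arm. Fatal-bleed rates over two years in the stroke-prevention trial tabulated in section 1.5 are 0.2% on the combination and 0.1% on placebo.

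- Active: 528 × 0.002 = 1.1
- Placebo: 528 × 0.001 = 0.5

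These are two-year figures, and study drug stops at the primary endpoint, so exposure here is shorter for most subjects. In the other direction, section 1.5 expects a higher baseline of serious bleeding in dialysis patients. Either way the counts are low. None of this says how many cases the trigger would miss, and the protocol holds no figure from which that could be worked out.

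**4. Upper bound on the reading load if the trigger is widened**

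Inputs: one-year control failure 0.54, a 25% reduction, and 22% annual loss (section 9.1); annual mortality 16% (section 1.3, read as mortality because it is compared there with 8% per year). Constant hazards are assumed.

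- Control: −ln(0.46) + (−ln(0.78)) = 0.777 + 0.248 = 1.025 per year, so mean time 1 / 1.025 = 0.98 years
- Active: 0.75 × 0.777 + 0.248 = 0.831 per year, so mean time 1 / 0.831 = 1.20 years

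This ignores truncation at study end and the final month of follow-up, and supports roughly one monitored year per subject. Then 1056 × 1 × 0.16 ≈ 169 deaths. Over the 54 months in the section 9.1 addendum (48 of recruitment plus 6 of follow-up), 169 / 54 ≈ 3.1 a month. That is the load if every death in the monitored period were read; the fix below covers only part of them.

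**The case against.** The strongest reply is that section 6.2.6 is a screen for quality control and leaves the definition alone. A center can class a bleed as fatal at any interval, and nothing in 6.2.6 removes that classification. This stands. A reader might infer that the two sections contradict each other; they do not. One defines a fatal bleed, and the other chooses which deaths get a second look.

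A reader might also infer that fatal bleeds outside the trigger are bound to go unnoticed. The documents do not support that. The section 4.3.1 panel reviews every recorded major or life-threatening bleed with no time window. A stroke on active treatment calls for imaging to exclude intracerebral hemorrhage. Hospital and emergency records are read with bleeding in mind, dialysis logs are checked for missed sessions, and nurses are asked when a patient is a doubtful historian. A bleed of any grade triggers the review, so it can add fatal bleeds as well as confirm them. If the bleed date counts, late-entered bleeds qualify too.

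These safeguards shrink the gap without closing it. The panel is not asked about cause of death. Record review needs a hospitalization or emergency visit, which a death at home does not produce. The 24-hour report brings the death to the coordinating center, but no rule sends it to a reviewer when no bleed is on file.

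The last tempting inference is that the active arm would look falsely safe. Treatment is masked, and if the same fraction of fatal bleeds is missed in both arms the risk ratio is unbiased and only the absolute difference shrinks. Time to death from any cause, which needs no attribution, is a secondary outcome. Section 1.5 also notes that none of the 451 dialysis patients on the equivalent combination in the unpublished German trial was reported to have died from bleeding.

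**Conclusion.** The point holds as a coverage gap of minor to moderate weight. The review is narrower than the definition it serves and falls short of its own stated purpose, because deaths with an earlier serious bleed, or with no separate bleed record, receive no central judgment on bleeding as the cause. This rests on the text alone.

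The number of deaths affected cannot be derived, no bias in the risk ratio is shown, and the primary patency analysis is unaffected. The case for acting is that bleeding is the main expected harm, fatal cases will be few on any assumption the protocol supports, and the reviewers and death reporting are already in place.

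**What to change.** Amend section 6.2.6 so that the same two reviewers, masked to arm and applying the section 4.3.1 definition, also review:

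1. deaths during participation that are reported as hemorrhage, stroke, or sudden or unknown cause, whether or not a bleed was recorded; and
2. deaths at any interval after a recorded major or life-threatening bleed.

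Keep the 30-day trigger for other bleeds and state that it runs from the date of the bleed, not the date of entry.

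The change concerns adjudication only and alters nothing in patient management. It costs a short amendment and somewhat more death files for centers to collect and reviewers to read, at most about three a month within the monitored period. Deaths after participation ends are learned of at closeout or from national databases, so their records may take extra effort to obtain. Some unexplained out-of-hospital deaths will remain unclassifiable and should be tabulated as such by arm.
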